10.1.2 Accrual

The study center treats approximately 6-7 patients monthly who would be eligible for enrollment in the trial. We estimate that 3-4 patients will enroll a month.

10.2 Safety population

The safety population is defined as all patients who receive at least 1 dose of either enzalutamide or ADT. This population will be used for all safety analyses as well as efficacy analyses.

10.3 Metabolic syndrome population

The metabolic syndrome population is defined as patients who have received at least 1 dose of either drug, have baseline values and at least 1 post-baseline assessment.

10.4 Secondary endpoint population

Defined as patients who have received at least 1 dose of either drug, have baseline values and at least 1 post-baseline assessment.

11. SAFETY ANALYSIS

The safety population will be used for the analysis of the toxicities and AEs. Individual toxicities will be summarized by their frequency and intensity for each treatment group. Safety will be evaluated by the incidence of AEs, severity and type of AEs, and by changes from baseline in the patient's vital

COMIRB/Protocol # 14-0909**Protocol Version:****4.27.2018 PI: [name]**

signs, weight, and clinical laboratory results using the safety population. Exposure to study drug and reasons for discontinuation will be tabulated.

Treatment related AEs that occur after administration of the first dose of study drug and through 30 days after the last dose of study drug will be tabulated. AEs will be tabulated according to the Medical Dictionary for Regulatory Activities (MedDRA) and will include the following categories:

- Drug-related AEs
- Grade 3 or higher AEs
- Grade 3 or higher drug-related AEs
- The most commonly reported treatment-emergent AEs (i.e., those events reported by $\geq 10\%$ of all patients)
- SAEs

A listing of AEs resulting in study discontinuation will be provided.

Descriptive statistics for the actual values of clinical laboratory parameters (and/or change from baseline in clinical laboratory parameters) will be presented for all scheduled measurements over time.

All concomitant medications collected from screening through the study period will be classified to preferred terms according to the World Health Organization (WHO) drug dictionary.

Additional safety analyses may be performed to most clearly enumerate rates of toxicities and to further define the safety profile of enzalutamide and ADT.

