In the randomized clinical trial in patients with metastatic castration-resistant prostate cancer who had previously received docetaxel, 1200 patients were enrolled. The most common adverse drug reactions ($\geq 5\%$) reported in patients receiving enzalutamide in the randomized clinical trial were asthenia/fatigue, back pain, diarrhea, arthralgia, hot flush, peripheral edema, musculoskeletal pain, headache, upper respiratory infection, muscular weakness, dizziness, insomnia, lower respiratory infection, spinal cord compression and cauda equina syndrome, hematuria, paresthesia, anxiety, and hypertension ³³. Severe, grade ≥ 3 adverse events, were reported in 47% patients receiving enzalutamide and 53% of patients receiving placebo. The most common adverse reaction leading to treatment discontinuation in the enzalutamide treated group was seizure, which occurred in 0.9% of the enzalutamide-treated patients compared to none (0%) of the placebo-treated patients. In the Phase III trial, 7 of 800 patients treated with enzalutamide experienced a seizure in comparison to 0 events in the placebo arm. The seizures occurred days 31-603 after drug initiation. No further seizures occurred after patients discontinued enzalutamide. Patients were never readministered enzalutamide while on study, and patients with a history of seizure have been excluded in additional studies. It is thought that the mechanism of seizure may be the inhibition of the GABA-gated chloride channel. It is suggested that enzalutamide may lower the seizure threshold but not directly contribute to these events. This trial will exclude patients with a predisposition to seizure, as the exclusion of this subset of patients should not have a known impact on altering the incidence of metabolic syndrome. Another notable adverse event associated with the enzalutamide treatment arm is fall and fall-related injuries. This occurred in 4.6% of patients enrolled in the randomized trial and assigned to the enzalutamide treatment group in comparison to 1.3% of patients treated with placebo. The mechanism of fall is not clear. Fall-related injuries are described as joint injuries, non-pathologic fractures, and hematomas.

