4. STUDY DESIGN

4.1 Overview of Study Design

This study is a multi-center, open label, randomized, phase II trial of the incidence of metabolic syndrome within 12 months in patients treated with enzalutamide in comparison with androgen deprivation therapy for treatment of advanced prostate cancer. This will include patients with biochemically recurrent disease, metastatic disease, and patients offered ADT as primary therapy if they are not candidates for local therapy. Fifty-six patients will be 1:1 randomized to one of two treatment arms with metastasis as a stratification factor. Patients will be treated for a 12-month period continuously and assessed for the development of metabolic syndrome at 3-month intervals.

Treatment will be administered for a 12-month period. Enzalutamide will be taken orally on each day of the cycle. Androgen deprivation therapy will be administered according to standard of care; however, there will be no intermittent dosing of this treatment. Acceptable forms of ADT must result in castrate levels of testosterone (<50ng/dL), and may include: leuprolide, goserelin, histerelin, triptorelin, degarelix, and surgical castration. Toxicity will be evaluated according to National Cancer Institute Common Terminology Criteria for Adverse Events (NCI CTCAE), Version 4.1 ³⁵. Metabolic syndrome will be diagnosed by assessing a patient's blood pressure, waist circumference, fasting glucose, high density lipoprotein (HDL), and triglyceride level and determined according to the Adult Treatment Panel III criteria ³⁶.

Analysis of bone turnover will include measurement of urinary N-telopeptide and serum bone-specific alkaline phosphatase. A dual-energy x-ray absorptiometry scan (DXA) will also be performed at enrollment, month 3 and EOT. This scan will provide information on bone density changes induced by treatment.

Quality of life questionnaires will be administered at each study visit. Physical function changes will be assessed via the Short Physical Performance Battery; the SPPB incorporates 3 validated portions to assess a patient's balance and mobility. Changes in systemic inflammation will be assessed via circulating hs-CRP levels. Additional collection of complete blood counts and chemistries will provide safety information. This testing will occur in the clinic setting every 3 months as well.

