10. STATISTICAL AND QUANTITATIVE ANALYSES

10.1 Statistical Methods

We estimate a 7% (2 patients) and 32% (9 patients) incidence of metabolic syndrome for enzalutamide and ADT treated patients based on historic data ⁷. Historical cross-sectional data would suggest that almost 50% of patients on ADT will develop metabolic syndrome, however, the trial population proposed will be pre-selected. Twenty-eight (28) patients in each of the two groups will provide 80% power to detect the 25% difference using a one-sided chi-square test with a significance level of 0.05 (actual alpha=0.054).

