12. ADVERSE EVENTS

12.1 Definitions

Definition of Adverse Events (AEs)

An adverse event (AE) is defined as any untoward medical occurrence in a subject administered a study drug and which does not necessarily have a causal relationship with this treatment. An AE can therefore be any unfavorable and unintended sign (including an abnormal laboratory finding), symptom, or disease temporally associated with the use of a study drug, whether or not related to the study drug.

An abnormality identified during a medical test (e.g., laboratory parameter, vital sign, ECG data, physical exam) should be defined as an AE only if the abnormality meets one of the following criteria:

- Induces clinical signs or symptoms.
- Requires active intervention.
- Requires interruption or discontinuation of study medication.
- The abnormality or investigational value is clinically significant in the opinion of the investigator.

All adverse events, whether or not related to the study drug, must be fully and completely documented.

Definition of Serious Adverse Events (SAEs)

An AE is considered "serious" if, in the view of either the investigator or sponsor, is unexpected and is potentially related to study participation and it results in any of the following outcomes:

- Results in death,
- Is life threatening (an AE is considered "life-threatening" if, in the view of either the investigator or sponsor, its occurrence places the subject at immediate risk of death. It does not include an AE that, had it occurred in a more severe form, might have caused death.),
- Results in persistent or significant disability/incapacity or substantial disruption of the ability to conduct normal life functions,
- Results in congenital anomaly, or birth defect,

- Requires inpatient hospitalization or leads to prolongation of hospitalization (hospitalization for treatment/observation/examination caused by AE is to be considered as serious),
- Other medically important events.

Serious Adverse Event Reporting

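### Section 11 joins a treatment-emergent time window to the words 'treatment related', contradicting its own list of AE tables, and its pooled 10% cut keeps one-arm events off the common-AE list

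*Combined protocol and SAP*

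**What the plan says.** Section 11 (Safety Analysis) states what will be tabulated: "Treatment related AEs that occur after administration of the first dose of study drug", up to 30 days after the last dose. The next sentence says AEs will be tabulated by MedDRA and gives five categories: drug-related AEs; grade 3 or higher AEs; grade 3 or higher drug-related AEs; common AEs; and SAEs. The common category reads "The most commonly reported treatment-emergent AEs (i.e., those events reported by" at least 10% of all patients). A listing of AEs that led to discontinuation is added.

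The same section also promises a summary of individual toxicities by frequency and intensity for each treatment group, and an evaluation of safety by the incidence, severity and type of AEs. Section 10.1.1 promises tables and descriptive statistics for AE data and states no causality limit. On collection, section 12.1 is explicit: "All adverse events, whether or not related to the study drug, must be fully and completely documented". Section 12.2 has the principal investigator supply all AEs, serious and non-serious, in a report.

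The setting is in section 4.1: "This study is a multi-center, open label, randomized, phase II trial", and "Fifty-six patients will be 1:1 randomized to one of two treatment arms". Section 4.5 has each AE assessed for a possible contribution by the study drug.

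**The concern.** Safety and tolerance of the two treatments is a secondary objective (section 2.2), and the treatments have different toxicity profiles. Two features of section 11 weaken that comparison.

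The first is attribution. Whoever judges whether an event is drug-related knows the arm. Events that investigators expect from one drug are more likely to be called related on that drug. If the tables hold only related events, part of any difference between arms reflects expectation. The text does not settle whether they do, so two programmers could build different tables from the same data.

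The second is the pooled threshold. A cut taken over both arms together is least sensitive to events confined to one arm, which are the events a two-drug safety comparison most needs to show.

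**Working it through.** **Attribution wording: two readings side by side**

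- *The lead sentence governs.* Only related events are tabulated. Grade 3 or higher AEs and grade 3 or higher drug-related AEs then become the same table, and the treatment-emergent category is cut down to related events.
- *The list governs.* Grade 3 or higher and treatment-emergent AEs are of any cause, and the drug-related categories are subsets. The words 'treatment related' in the lead sentence are then wrong. The time window, first dose to 30 days after last dose, is the usual one for treatment-emergent events, which suggests loose wording.

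The second reading is the more plausible, but a gap remains under it. An event that is grade 1-2, non-serious, judged unrelated, seen in fewer than 6 patients and not a cause of discontinuation fits none of the five categories and is not in the discontinuation listing.

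The SAE category may carry the same ambiguity. The definition in section 12.1 requires an SAE to be unexpected and potentially related, while the reporting text under the same heading covers SAEs whether or not related to enzalutamide.

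**Pooled threshold: inputs**

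- 56 patients, 1:1, so 28 per arm (sections 4.1 and 10.1). The stated design behind the 28 reproduces: an uncorrected one-sided chi-square at 7% v 32% has exact power 81.1% and exact size 0.0538, against the stated 80% and 0.054.
- Cut of 10% of all patients (section 11).
- Assumed true event rates of 15% v 2% and 20% v 2%. These are illustrative and do not come from the documents.

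**Step 1: the cut in patients**

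- Pooled: 0.10 × 56 = 5.6, so 6 patients. The cut stays at 6 while at least 51 patients are dosed (0.10 × 51 = 5.1); at 50 it becomes 5.
- Either arm: 0.10 × 28 = 2.8, so 3 patients in one arm.

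**Step 2: the largest one-arm event left off**

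- 5/28 = 17.9% v 0/28 gives 5/56 = 8.9%, below the cut. Fisher's exact test on 5/28 v 0/28 gives p = 0.051 two-sided and 0.026 one-sided.

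**Step 3: chance of being listed**

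Let X ~ Bin(28, p1) and Y ~ Bin(28, p2) be the numbers of patients with the event in the two arms.

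- Pooled rule: P(X + Y ≥ 6), by convolution of the two binomials.
- Either-arm rule: 1 − P(X ≤ 2) × P(Y ≤ 2).

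| Assumed rates | Missed, pooled | Listed, pooled | Listed, either arm |
|---|---|---|---|
| 15% v 2% | 0.66 | 0.34 | 1 − 0.187 × 0.982 = 0.82 |
| 20% v 2% | 0.40 | 0.60 | 1 − 0.061 × 0.982 = 0.94 |

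**Step 4: falls**

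Section 1.5 gives falls and fall-related injuries in 4.6% on enzalutamide v 1.3% on placebo. At 28 per arm, 28 × 0.046 = 1.3 and 28 × 0.013 = 0.4 patients are expected. The chance of at least one on enzalutamide is 1 − (1 − 0.046)^28 = 0.73. The chance that falls reach the common-AE list is 0.006 under the pooled rule and 0.14 under the either-arm rule.

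**The case against.** The strongest reply is that section 11, read as a whole, does not restrict its tables to related events. The sentence that introduces the list speaks of AEs without a qualifier. Naming drug-related AEs as separate categories makes sense only if the others are of any cause. A reading that makes two listed tables identical should be rejected. Sections 10.1.1 and 11 also promise AE summaries with no stated causality limit, including toxicities by arm with no frequency cut. This largely stands. A reader might infer that the plan limits all AE tables to related events, or that arm-specific harms would be removed from the comparison. The documents do not support either inference. What the reply leaves is a contradiction in the text, and general promises that specify no table. 'Toxicities' is not defined and could itself be taken to mean related events.

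On the threshold, the reply is that the cut defines one category of five. An event left off the common list still appears if it is grade 3 or higher, drug-related or serious. The cut is also a reporting choice for a descriptive list, and no between-arm AE test is planned. That stands too: the probabilities above are the chance of missing that list, not of missing the safety comparison.

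Falls are a tempting example, since section 1.5 says "The mechanism of fall is not clear" and a fall is easily judged unrelated. They do not illustrate the pooling problem. At the cited rates they would miss an either-arm 10% cut about 86% of the time (1 − 0.14), so rarity keeps them off, not pooling. A grade 3 or higher fall has an any-cause category if the list governs. The rates also come from castration-resistant patients previously given docetaxel, with a placebo control, not from this population or against ADT.

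**Conclusion.** The point holds, at minor severity. Section 11 contradicts itself on whether its AE tables depend on attribution, and in an open-label trial that should be settled before tables are programmed. Even on the generous reading, low-grade, non-serious, unrelated events in fewer than 6 patients have no assured place in the listed categories.

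The pooled cut leaves off the common-AE list an event seen in up to 17.9% of one arm and none of the other. Moving to an either-arm cut raises the chance of listing by 0.48 at 15% v 2% (0.82 − 0.34) and by 0.34 at 20% v 2% (0.94 − 0.60). These figures assume that all 56 patients are dosed, 28 per arm, and that the illustrative rates apply.

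**What to change.** In section 11:

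1. Replace the opening words 'Treatment related AEs that occur' with 'All treatment-emergent AEs, regardless of attribution, that occur'. State that the tables are by treatment arm, with drug-related AEs as a subset. This also closes the gap for low-grade unrelated events.
2. Replace '10% of all patients' with '10% of patients in either treatment group'.

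Optionally, show falls, fall-related injuries and seizures by arm at any frequency and whatever the attribution. The reason is their rarity and their mention in section 1.5, not the pooled threshold.

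The cost is slightly longer AE tables. No new data are needed, because section 12.1 already has every AE documented.

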11.1 Oversight and Monitoring

The Lead Principal Investigator (PI) will be responsible for monitoring the trial per the trial monitoring plan, in addition to overseeing the safety and efficacy of the trial, executing the DSM plan, and complying with all reporting requirements to local and federal authorities. This oversight will be accomplished through additional oversight from the Data and Safety Monitoring Committee (DSMC) at the University of Colorado Cancer Center (CU Cancer Center). The DSMC is responsible for ensuring data quality and patient safety for all clinical studies at the CU Cancer Center. A summary of the DSMC's activities is as follows:

- Conduct of internal audits
- Ongoing review of all serious adverse events (SAEs), unanticipated problems (UAPs) and reportable adverse events (AEs)
- Has the authority to close and/or suspend trials for safety or trial conduct issues
- May submit recommendations for corrective actions to the CU Cancer Center's Executive Committee

Per the CU Cancer Center Institutional DSM Plan, SAEs, UAPs and reportable AEs are reported to the DSMC, IRB and the sponsor per study protocol. All SAEs, UAPs and reportable AEs are to be reported to the DSMC within 5 business days of receiving notification of the occurrence.

Each subject's treatment outcomes will be discussed by the Site PI(s) and appropriate staff at regularly scheduled disease-oriented working group meetings. Data regarding number of subjects, significant toxicities, dose modifications, and treatment responses will be discussed and documented in the meeting's minutes.

The Lead PI in this multi-site trial is responsible for organizing and conducting monthly teleconferences with all participating sites. The Lead PI will also be responsible for including data from all of the participating sites to include the minutes from these regularly scheduled teleconferences between the Lead PI and the sites within the overall trial's six-month DSM report.

The Lead PI will provide a DSM report to the CU Cancer Center DSMC on a six-month basis. The DSM report will include a protocol summary; current enrollment numbers; summary of toxicity data to include specific SAEs, UAPs and AEs; any dose modifications; all protocol deviations; and protocol amendments. The DSM report to the DSMC will also include, if applicable, the results of any efficacy data analysis conducted, as well as any internal DSMB reports. Results and recommendations from the review of this six-month report by the DSMC will then need to be submitted by the site to the IRB of record at the time of continuing review.

12. ADVERSE EVENTS

12.1 Definitions

Definition of Adverse Events (AEs)

An adverse event (AE) is defined as any untoward medical occurrence in a subject administered a study drug and which does not necessarily have a causal relationship with this treatment. An AE can therefore be any unfavorable and unintended sign (including an abnormal laboratory finding), symptom, or disease temporally associated with the use of a study drug, whether or not related to the study drug.

An abnormality identified during a medical test (e.g., laboratory parameter, vital sign, ECG data, physical exam) should be defined as an AE only if the abnormality meets one of the following criteria:

- Induces clinical signs or symptoms.
- Requires active intervention.
- Requires interruption or discontinuation of study medication.
- The abnormality or investigational value is clinically significant in the opinion of the investigator.

All adverse events, whether or not related to the study drug, must be fully and completely documented.

Definition of Serious Adverse Events (SAEs)

An AE is considered "serious" if, in the view of either the investigator or sponsor, is unexpected and is potentially related to study participation and it results in any of the following outcomes:

- Results in death,
- Is life threatening (an AE is considered "life-threatening" if, in the view of either the investigator or sponsor, its occurrence places the subject at immediate risk of death. It does not include an AE that, had it occurred in a more severe form, might have caused death.),
- Results in persistent or significant disability/incapacity or substantial disruption of the ability to conduct normal life functions,
- Results in congenital anomaly, or birth defect,

- Requires inpatient hospitalization or leads to prolongation of hospitalization (hospitalization for treatment/observation/examination caused by AE is to be considered as serious),
- Other medically important events.

Serious Adverse Event Reporting

For patients on enzalutamide therapy, within 48 hours of awareness of a serious adverse event, whether or not related to enzalutamide, the Investigator will complete and submit a Medwatch 3500A Form, containing all required information (reference 21 CFR 312.32). The Investigator will submit a copy of this MedWatch 3500A form to FDA and Astellas by either e-mail or fax, within the same timeframe if subject is on enzalutamide. If submission of this SAE to FDA or Astellas or is not possible within 48 hours, the Investigator's local drug safety contact (IRB, etc.) should be informed by phone.

The SAE documentation, including the Medwatch 3500A Form and available source records should be emailed or faxed to:

Astellas Pharma Global Development – United States
Email: [contact]
[contact]

The following minimum information is required:

- Study number/IIT regulatory identifier
- Subject number, sex and age
- The date of report
- A description of the SAE (event, seriousness of the event)
- Causal relationship to the study drug

Follow-up information for the event should be sent within promptly (within 7 days) as necessary.

All SAEs , regardless of treatment arm, will be reported to the University of Colorado DSMC within 48 hours of awareness of the event.

Procedure in Case of Pregnancy

The effect of enzalutamide in pregnant and lactating women is not known, and the exposure of a fetus or nursing infant is considered a potential risk. Enzalutamide can cause fetal harm when administered to a pregnant woman based on its mechanism of action. Subjects receiving enzalutamide are advised to use 2 acceptable methods of birth control (one of which must include a condom as a barrier method of contraception) starting at the time of screening for an enzalutamide study and continuing throughout the course of treatment and for at least three months after enzalutamide is discontinued.

If during the conduct of the clinical trial, a male subject impregnates his partner, the subject should report the pregnancy to the Investigator. The Investigator should report the pregnancy to the Sponsor as an SAE within 24 hours of awareness of the event. The expected date of delivery or expected date of the end of the pregnancy, last menstruation, estimated fertility date, pregnancy result and neonatal data etc., should be included in this information.

The Investigator should report the outcome of the pregnancy (independent of outcome, eg. full term delivery, pre-term delivery, spontaneous abortion, induced abortion, stillbirth, death of newborn,

COMIRB/Protocol # 14-0909

Protocol Version:

4.27.2018 PI: [name]

congenital anomaly [including anomaly in a miscarried fetus, etc] in accordance with the same reporting procedure as for SAEs. The date of outcome of the pregnancy, gestational age, date of birth and neonatal data etc., should be included in this information.

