3.2 Secondary Endpoints

- Incidence of metabolic syndrome within 6 months, as defined by the ATP III, in patients treated with enzalutamide versus patients treated with standard testosterone-lowering ADT
- Change in bone density, as measured by a DXA scanner
- Change in bone turnover as measured by bone-specific alkaline phosphatase and N-telopeptide
- Change in body composition (fat distribution as measured on CT)
- Change in QOL, as measured by the FACT-P and SHIM
- Time to PSA progression and time to radiographic progression. Progression will be defined as lack of clinical benefit in the setting of either rising PSA, growth of visceral or soft tissue metastasis, or development of new bone metastasis as defined per protocol
- Incidence of developing individual risk factors, or components, which comprise metabolic syndrome
- Change in inflammatory markers as measured by serum hs-CRP

- Safety and tolerability as assessed by regular recording of toxicities via physical exam and laboratory analysis using the CTCAE v4.1 guidelines
- Change in physical function as measured by the Short Physical Performance Battery

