4.5 Dose Modification Guidelines

Patients will be assessed for toxicities at each study visit, every 3 months. Patients may be evaluated more frequently at the discretion of the treating provider. Toxicities are to be assessed according to the NCI CTCAE, version 4.1. Each AE should be assessed for potential contribution by the study drug. If a patient experiences a grade ≥ 3 toxicity on enzalutamide or an intolerable side effect, withhold dosing for one week or until symptoms improve to grade ≤ 2 . Dosing may resume at the same, or a reduced dose, (per treating physician discretion) for a maximum dose reduction to 80mg daily. Once a dose reduction has occurred, the patient may not re-escalate to a higher dose.

There are no dose modifications for ADT. As stated, this therapy must be dosed continuously and may not be given on an intermittent basis.

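### Section 12.1 lets a dosing interruption make a test abnormality an adverse event, and section 4.5 makes that route automatic at grade 3 or higher on enzalutamide only; a derived-grade table by arm would remove the difference cheaply

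*Combined protocol and SAP*

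**What the plan says.** Section 12.1 (Definitions) says that an abnormality found on a test, with laboratory parameters and vital signs among its examples, "should be defined as an AE only if the abnormality meets one of the following criteria". The four criteria are that it causes signs or symptoms, that it needs active intervention, "Requires interruption or discontinuation of study medication", or that the investigator considers it clinically significant. The wording is the same for both arms.

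Section 4.5 (Dose Modification Guidelines) treats the arms differently. For enzalutamide: "If a patient experiences a grade ≥ 3 toxicity on enzalutamide or an intolerable side effect, withhold dosing for one week". For the comparator: "There are no dose modifications for ADT", and "this therapy must be dosed continuously and may not be given on an intermittent basis".

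Section 3.2 defines the safety endpoint as "Safety and tolerability as assessed by regular recording of toxicities via physical exam and laboratory analysis using the CTCAE v4.1 guidelines". Section 2.2 lists safety and tolerance among the objectives that compare enzalutamide with ADT. Section 11 summarises individual toxicities by frequency and intensity in each treatment group and lists grade 3 or higher AEs as a tabulated category. For laboratory data it adds: "Descriptive statistics for the actual values of clinical laboratory parameters (and/or change from baseline in clinical laboratory parameters) will be presented".

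**The concern.** Whether an abnormal value counts as an AE should not depend on which arm's dosing rules apply. Read together, sections 12.1 and 4.5 give grade 3 or higher values a guaranteed route into the AE record on enzalutamide and no equivalent on ADT. For an ADT patient whose value causes no symptoms, needs no treatment and does not end therapy, the only route left is the investigator's opinion. The trial is open label (section 4.1), so that opinion is formed knowing the treatment.

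The grade 3 or higher AE table is where the two rules diverge, and any distortion would run against enzalutamide. With 28 men per arm, a difference of one or two men in such a table can colour the tolerability comparison. The laboratory summaries planned in section 11 would not necessarily reveal it, because means and changes from baseline need not show how many men reached grade 3.

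**Working it through.** The plan states no figure on this point, so there is none to reproduce. The check compares the text for the two arms and then gives a bounded illustration.

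**Routes into the AE record for a grade 3 or higher test value**

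| Criterion in 12.1 | Enzalutamide | ADT |
|---|---|---|
| Signs or symptoms | if present | if present |
| Active intervention | if needed | if needed |
| Interruption | met by rule, if toxicity in 4.5 covers laboratory findings | no dose modification provided for |
| Discontinuation | open (4.2, 7.8) | open (4.2, 7.8), but tied to unacceptable toxicity or withdrawal, not to grade 3 as such |
| Clinically significant | investigator's opinion | investigator's opinion |

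Only the interruption row differs. It affects the outcome only for values that no other route captures.

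**Size**

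Inputs:
- n = 28 per arm (section 10.1).
- q = fraction of men, equal in both arms, with an asymptomatic, untreated grade 3 or higher value that does not end therapy. Assumed.
- f = fraction of those values on ADT that the investigator calls clinically significant. Assumed.
- All such values on enzalutamide are recorded, because the rule is followed.

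Formulas: recorded on enzalutamide = n × q; recorded on ADT = n × q × f; gap = n × q × (1 − f).

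The documents give neither q nor f. The nearest figures are the grade 3-4 rates on enzalutamide in section 1.5: 1% for neutropenia and 0.3% for raised transaminases. Their sum, 1.3%, is the first row below. It assumes that no man had both and that none of these values had symptoms or treatment. It covers only those two tests.

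| q | Enzalutamide, 28 × q | ADT, f = 1 | ADT, f = 0.5 | ADT, f = 0.25 |
|---|---|---|---|---|
| 1.3% (section 1.5) | 0.36 | 0.36 | 0.18 | 0.09 |
| 5% (assumed) | 1.4 | 1.4 | 0.7 | 0.35 |
| 10% (assumed) | 2.8 | 2.8 | 1.4 | 0.7 |
| 20% (assumed) | 5.6 | 5.6 | 2.8 | 1.4 |

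At f = 1 the gap is zero for every q. At q = 1.3% it cannot exceed 0.36 of a man, even if no ADT value is judged significant (28 × 0.013 × 1 = 0.36). At q = 10% and f = 0.5 it is 2.8 − 1.4 = 1.4 men. At q = 20% and f = 0.25 it is 5.6 − 1.4 = 4.2 men. The last two are illustrations, not estimates.

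**The case against.** The strongest reply turns on the word toxicity, which section 4.5 uses without definition. The rule comes directly after an instruction to assess each AE for a contribution by the study drug, and dosing is held "toxicity on enzalutamide or an intolerable side effect, withhold dosing for one week or until symptoms improve". On that narrow reading a bare asymptomatic value triggers no hold: it would have to be a recognised event first, and the route becomes circular. On the broad reading, supported by section 3.2, laboratory findings are toxicities. But section 11 already plans to summarise individual toxicities by arm, arguably without passing through the AE definition. Either way the point shrinks.

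Both parts have weight, and neither closes the gap. The text does not choose between the readings. The individual-toxicities sentence does not say whether its grades come from measured values or from recorded AEs. The grade 3 or higher AE table passes through section 12.1 on any reading.

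Four further objections stand and set the limits of the point:
- A reader might infer that a grade 3 value on ADT cannot become an AE. It can, because three criteria apply equally to both arms and discontinuation is open on ADT.
- A reader might infer that the metabolic results are biased. They are not: section 7.1 scores metabolic syndrome from measurements or drug treatment against fixed thresholds, without reference to AE status.
- The section 1.5 rates come from a post-docetaxel, castration-resistant population. Section 5.2 of this trial excludes men with low neutrophils, low platelets or raised transaminases.
- AE reporting is descriptive (section 10.1.1), so no planned test is affected.

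**Conclusion.** The inconsistency is real but minor. If toxicity in section 4.5 includes laboratory findings graded by CTCAE, grade 3 or higher test values are recorded as AEs by rule on enzalutamide and partly by unblinded judgement on ADT. The difference is in the guaranteed route, not in eligibility. It concerns only asymptomatic, untreated values that do not end therapy, and it reaches only the AE tables of section 11.

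Its size cannot be determined from the documents. It ranges from zero, when every such ADT value is judged significant, to well under one man per arm at the section 1.5 rates for two laboratory tests. A gap of one or more men requires rates of silent grade 3 values that the documents do not supply. The ratio of recorded rates, 1/f within this class of values, should not be read as a distortion of the whole AE table. The point is worth acting on because the repair is cheap and uses data already collected.

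**What to change.** In section 11:
- Derive CTCAE grades from the recorded laboratory values and blood pressure at the scheduled visits common to both arms. Leave out unscheduled tests, whose frequency may differ by arm.
- Grade glucose from fasting samples only; Table 1 does not require fasting at the end-of-study visit.
- State how any grade that depends on more than the measured value will be handled.
- Tabulate worst post-baseline grade and shift from baseline by arm, and base the between-arm reading of laboratory and vital-sign toxicity on that table.
- State that the summary of individual toxicities uses these derived grades for laboratory and vital-sign findings.

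In section 12.1, keep all four criteria and add a fifth: any grade 3 or higher test value is recorded as an AE in both arms. The interruption criterion should stay, because removing it could lose lower-grade abnormalities that led to a hold, for instance as an intolerable side effect under section 4.5.

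The cost is a few sentences, one more table, and a few more AE records on ADT (1.4 men in the illustration with q = 10% and f = 0.5). No extra visits or samples are needed, and no dosing rule changes.
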